### **8.1.3. Methodology for Other Endpoints**

#### **8.1.3.1. Demographics, Medical History, and Baseline Characteristics**

Disposition counts (enrolled, randomized, etc) will be tabulated. Statistical tests will not be employed.

Frequency counts and proportions will be compiled for:

- Sex

- Race
- Racial designation (limited to subjects choosing race = Asian)
- Ethnicity
- Smoking status (current smoker, past smoker, never smoked)
- Age group (18 to <50, 50 to 64, and 65 to <86 years)
- Alcohol use (yes/no)
- Physical examination
- Colonization status on Day 1 (each anatomical site and combined anatomical sites)
- Medical history
- CCI score (0, 1, 2, and  $\geq 3$ )
- ASA score

The denominators will be the number of subjects in the vaccine group, except the denominators for racial designation, which will be the number of subjects in the vaccine group who choose race = Asian.

The summary statistics n, mean, standard deviation, median, minimum, and maximum will be compiled for:

- Age
- BMI
- Units of alcohol (in units per week, limited to subjects reporting alcohol use)
- ASA score
- CCI score
- Charlson comorbidity 10-year mortality probability
- Vital signs
- Elapsed days from vaccination to index surgery

Medical history will be summarized by preferred term and system organ class. The number and percentage of subjects with at least 1 diagnosis of each preferred term, arranged by system organ class, will be tabulated for each vaccine group. The denominator for the percentages will be the number in the vaccine group or the total sample, respectively, excluding subjects for whom medical history was not collected. “Overall no significant history” will be included as a distinct category.

Physical examination findings will be summarized by the number and percentage of subjects with an “abnormal” score. The denominator will be the number of subjects with either “normal” or “abnormal.”

Statistical analyses for demography are summarized in [Section 8.2.3.1](#).

### **8.1.3.2. Index Surgery and Hospitalization**

The number and proportions of responses in each category will be compiled where exactly 1 choice is selected. Vaccine groups will be compared using the CMH test, with site as a stratification factor. “Other” will be retained as a category. This analysis applies to:

- *S aureus*/MRSA carriage evaluation performed
- Preoperative skin preparation
- Index surgery (initial or revisional)
- Wound classification
- Primary incision site
- Primary skin closure type
- Graft type
- Implant material (type and composition)
- Intrawound application of antibiotic
- Prophylactic antibiotics administered within 1 hour before incision
- Prophylactic antibiotics readministered during the index surgical procedure
- Index surgery modified to be a staged procedure, performed on separate days
- Requirement for index surgery reoperation/revision
- Specialty of the surgeon (levels defined in [Section 6.3.2](#))
- Evidence of malignancy during the index surgery

- Evidence of infection during the index surgery
- Capillary or serum glucose value before surgery
- Capillary or serum glucose value after surgery
- Temperature after surgery, using the categories in [Table 4](#)
- Any temperature, defined as  $\geq 38.0^{\circ}\text{C}$ , after surgery
- Been in an ICU
- At least 1 readmission to hospital
- Number of readmissions to hospital

Separate statistics will be compiled for subjects who were readmitted. The denominators will be the number of subjects who were readmitted, except as noted.

- At least 1 readmission was related to complications of the index surgery
- Additional surgery required in at least 1 readmission; the denominators will be the number of subjects whose readmission was related to complications of the index surgery
- Been in an ICU in at least 1 readmission
- Not discharged; ongoing hospitalization

The numbers and proportions of responses in each category will be compiled for responses where more than 1 level may be selected, but no statistical comparisons will be performed because some subjects may appear in more than 1 level. “Other” will be retained as a category. This applies to the following:

- Indication for surgery
- Decolonization measures, limited to subjects with any such measures
- Incision site hair removal method
- Implanted devices
- Specialty of surgeon
- Vertebrae fused

The denominators for the proportions will be the number of subjects, except as noted.

Descriptive statistics (n, mean, standard deviation, median, minimum, and maximum) will be compiled for numeric variables:

- Glucose value on the day of surgery, both fasting and nonfasting
- Glucose value on the day after surgery, both fasting and nonfasting
- Change in fasting glucose value
- Intraoperative blood loss
- Duration of surgery
- Number of vertebrae fused
- Duration of hospitalization
- Number of days in an ICU for the index visit (limited to subjects in intensive care)
- Number of days in an ICU during all readmissions (limited to subjects with at least 1 readmission)

Glucose statistics will be compiled by fasting status (fasting and nonfasting). If fasting status is unknown, then the value will be assumed to be nonfasting.

Vaccine groups will be compared using the van Elteren test, with site as the blocking factor, for duration of surgery, intraoperative blood loss, all glucose responses, duration of hospitalization, number of vertebrae fused, number of days in an ICU for the index visit, total number of days in an ICU during readmission, and total number of days hospitalized for readmissions.

Statistical analyses are summarized in [Section 8.2.3.2](#).

### **8.1.3.3. Healthcare Utilization**

Healthcare utilization variables whose units are days (eg, number of days in an ICU) will be summarized by sample size, mean, standard deviation, median, minimum, and maximum. Vaccine groups will be compared using the van Elteren test, with site as the stratification variable.

Categorical variables (eg, interventional procedures, discharge disposition) will be summarized by frequency counts and proportion of subjects in each category. If a subject has more than 1 hospital admission leading to more than 1 response, only the earliest hospital admission will be included in the analysis. Vaccine groups will be compared using the CMH method, with site as the stratification variable.

The number of service visits will be summarized by sample size, mean, standard deviation, median, minimum, and maximum. Vaccine groups will be compared using the van Elteren test.

The number of rehabilitation/physical therapy visits will be summarized by sample size, mean, standard deviation, median, minimum, and maximum. Vaccine groups will be compared using the van Elteren test.

Zeroes will not be imputed to subjects without the indicated response, eg, number of days in a skilled nursing facility.

All healthcare variables will be reanalyzed, but limited to subjects from the mITT efficacy population who have at least 1 PDI. Subjects with more than 1 PDI may be included in more than 1 analysis. There will be 6 additional analyses, 1 for each type of PDI (BSI and/or deep incisional or organ/space SSI, SSI, or ISA disease) by 2 windows (1-90 and 1-180 days). Vaccine groups will be compared in numeric variables using the Mann-Whitney test and compared in categorical variables using the Fisher exact test. The statistical tests will not incorporate site because the number of PDIs per site will be small or zero.

Statistical analyses for healthcare utilization are summarized in [Section 8.2.3.3](#).

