### **6.3.3. Healthcare Utilization**

The healthcare utilization endpoints include:

- Location prior to hospital admission.
- Days in hospital.
- Ongoing in hospital (ie, not discharged).

- Discharge disposition:
  - Home self-care
  - Home healthcare
  - Rehabilitation facilities
  - Nursing home/skilled nursing care facility/nursing home
  - Death
  - Other
- Readmission related to complications of the index surgery.
- Proportion of readmissions to hospital.
- Proportion of readmissions to hospital related to complications of the index surgery.
- Proportion of subjects with additional surgery (the denominator will be the number readmitted for complications).
- Proportion in the ICU during readmission (denominator is the number of readmitted subjects).
- Number of days in the ICU, limited to subjects with hospital readmission related to complications for surgery.
- Proportion of subjects discharged from the hospital after readmission (denominator is the number of readmitted subjects).
- Total duration of hospitalization from the index surgery and any readmissions.
- Total days in an ICU from the index surgery and any readmissions.
- Number of rehabilitation/physical therapy visits as an outpatient.
- Inpatient days in rehabilitation facility or skilled nursing facility after discharge.
- Number of service visits (meaning skilled nursing home/skilled nursing facility or rehabilitation facility); discharges from the hospital to either of these will not count as a service visit.

The duration of each hospitalization episode will be the last day minus the first day, plus 1. Duration will be missing for episodes ending as “ongoing.”

Statistical methodology for healthcare utilization is described in [Section 8.1.3.3](#).

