**Table 24. Summary of Healthcare Utilization Analyses**

Endpoint	Population	Statistical Method	Stratification	Missing Data	Interpretation/Comments
Categorical healthcare utilization: 
 
• location prior to hospital admission
 
• ongoing hospitalization, yes/no
 
• discharge disposition
 
• proportion of readmissions to hospital
 
• proportion of readmissions related to complications of index surgery
 
• additional surgery
 
• proportion in an ICU in readmission
 
• proportion discharge after readmission
 
	mITT	CMH	Site	N/A	Impact of vaccination on subsequent healthcare use
Numeric healthcare utilization: 
 
• duration of hospitalization
 
• number of readmissions related to complications of index surgery
 
• number of days in the ICU
 
• total hospitalization from index surgery and any readmissions
 
• total days in ICU from index surgery and any readmissions
 
• number of service visits
 
• number of inpatient days in rehabilitation or nursing facility
 
	Any subject with PDI	Mann-Whitney	N/A	N/A	Impact of vaccination on subsequent healthcare use, limited to subjects with PDIs  Performed for PDIs in 1-90 and in 1-180 days

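### SAP 8.1.3.3 and 8.1.3.2 score the same three exploratory readmission outcomes by different rules in the same mITT population

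*SAP*

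**What the plan says.** SAP 8.1.3.3 (Healthcare Utilization) summarises categorical variables by the number and proportion of subjects in each category. Where a subject's several admissions yield more than one response, "only the earliest hospital admission will be included in the analysis". Vaccine groups are then compared by the CMH method stratified by site.

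SAP Table 24 names the categorical variables in the mITT population. They include "proportion of readmissions related to complications of index surgery", additional surgery and "proportion in an ICU in readmission". SAP 8.1.3.3 and Table 24 also repeat the analyses in subjects with a protocol-defined infection (PDI), for three endpoint types and two time windows.

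SAP 8.1.3.2 (Index Surgery and Hospitalization) tabulates the same three variables for readmitted subjects, with a different rule:
- "At least 1 readmission was related to complications of the index surgery"
- "Additional surgery required in at least 1 readmission"
- "Been in an ICU in at least 1 readmission"

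SAP 8.2.3.2 runs the 8.1.3.2 variables in the safety, mITT efficacy and PP efficacy populations. SAP 8.2.3.3 runs the healthcare variables in the mITT efficacy population.

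**The concern.** Two sections of one SAP give different derivations for the same three variables in the same population, and nothing says which governs. The study report could carry two tables with different proportions for one outcome.

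The earliest-admission rule is also hard to program, because the SAP does not say whether the earliest hospital admission is the index admission or the first readmission.

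Comparing healthcare use between vaccine groups is a stated exploratory objective, so what is at stake is the clarity and accuracy of those tables. No primary or secondary efficacy result depends on the rule.

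**Working it through.** No sample size, power or error rate in the documents depends on this rule, so there is no planned figure to reproduce. The check is a comparison of texts, followed by an illustration on assumed inputs.

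**Step 1: are they the same variables?**

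| Variable | SAP 8.1.3.3 with Table 24 | SAP 8.1.3.2 |
|---|---|---|
| Complication-related readmission | Earliest admission, if responses differ | Any readmission |
| Additional surgery | Earliest admission, if responses differ | Any readmission |
| ICU in readmission | Earliest admission, if responses differ | Any readmission |

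The unit is the subject in both sections. For ICU, the denominator is readmitted subjects in both SAP 6.3.3 and 8.1.3.2. For additional surgery, SAP 6.3.3 has "Proportion of subjects with additional surgery (the denominator will be the number readmitted for complications", which matches 8.1.3.2. The mITT efficacy population is common to both analyses. The derivation rule is therefore the difference that matters.

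**Step 2: what does each reading of the earliest admission do?**

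- *Index admission.* The three variables describe readmissions. The index admission is not one, so they have no value to score.
- *First readmission.* A subject whose first readmission does not qualify but whose later one does is scored as no in Table 24 and as yes in 8.1.3.2. Subjects with one readmission, or whose first readmission qualifies, are unaffected.

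**Step 3: illustration for the first-readmission reading.** Neither input is in the documents; both are assumptions.

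- q = share of readmitted subjects who have a second readmission, taken as 0.1 to 0.3.
- p = chance that a given readmission qualifies, taken as 0.2 to 0.6, independent between readmissions, with at most two readmissions per subject.

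Subjects positive on the first readmission: p. Subjects ever positive: p + q(1 − p)p. Share of ever-positive subjects missed: 1 − p / [p + q(1 − p)p] = q(1 − p) / [1 + q(1 − p)].

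- Lowest: q = 0.1, p = 0.6 gives 0.04 / 1.04 = 3.8%.
- Highest: q = 0.3, p = 0.2 gives 0.24 / 1.24 = 19.4%.

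| | p = 0.2 | p = 0.4 | p = 0.6 |
|---|---|---|---|
| q = 0.1 | 7.4% | 5.7% | 3.8% |
| q = 0.2 | 13.8% | 10.7% | 7.4% |
| q = 0.3 | 19.4% | 15.3% | 10.7% |

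Positive correlation between a subject's readmissions would lower these shares; third and later readmissions would raise them. The formula suits complication-related readmission and ICU. For additional surgery the denominator is itself subjects readmitted for complications, so the earliest-admission rule can remove a subject from the denominator as well as the numerator, and the proportion need not fall.

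**Step 4: where are later events still counted?**

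- SAP 8.1.3.2 counts all three variables over any readmission, and also tabulates whether the index surgery needed reoperation or revision. SAP 8.2.3.2 repeats these analyses by infection status in mITT and PP.
- The numeric rows of Table 24 count complication-related readmissions and total ICU days over the index stay and all readmissions. They have no row for reoperations, so within Table 24 additional surgery appears only as a categorical variable.
- SAP 8.1.2.1 analyses all deaths in the safety population, with attribution to *S aureus* by the adjudication committee.

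**The case against.** The strongest reply is that the rule need not reach these variables. It is conditional on more than one response. The examples of categorical variables given with it are interventional procedures and discharge disposition, for which one response per subject is sensible. SAP 6.3.3 describes additional surgery as a proportion of subjects, which can be read as ever or never, so that each subject has one response and the rule is not triggered. That reading is possible, but the text does not state it. The rule covers categorical healthcare variables without exception, and Table 24 lists these three as categorical.

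The reply also says that little is lost, since the any-readmission results will be produced in mITT anyway and the objective is exploratory. SAP 8.1.3.5 records that the study met futility at its interim analysis and ceased enrollment. This stands, and it is why the point is minor.

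A reader might infer more than the documents support:
- *That later readmissions, reoperations and ICU stays are lost from the report.* They are not, as Step 4 of the working shows. The undercount is confined to the categorical rows of Table 24 and their PDI-only repeats.
- *That deaths are missed.* SAP 8.1.3.2 has no any-admission rule for death, so there is no conflict on it. Only the death level of discharge disposition could be affected, and deaths have their own safety analysis.
- *That a vaccine effect is diluted.* If a share s of events is missed in both groups, with true proportions a and b, the ratio is (1 − s)a / [(1 − s)b] = a / b. The absolute difference shrinks by the factor 1 − s, but the relative effect is unchanged. The documents give no reason to expect different losses by group.

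**Conclusion.** The inconsistency is real, and the rule in SAP 8.1.3.3 is wrong as written for complication-related readmission, additional surgery and ICU in readmission. On one reading it can undercount them relative to SAP 8.1.3.2; on the other it cannot be applied. The conclusion rests on the wording and on the shared mITT population, not on any assumed rate.

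The size is unknown because the documents give no repeat-admission rate. The range of 3.8% to 19.4% of subjects with an event is an illustration on assumed inputs, not an estimate. A similar loss in the PDI-only repeats is possible but cannot be sized either. Severity is minor: the analysis is exploratory, and the events remain visible in other planned analyses.

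**What to change.** In SAP 8.1.3.3, score complication-related readmission, additional surgery and ICU in readmission as yes if present in any readmission, with a cross-reference to 8.1.3.2 so that both sections share one derivation. Apply the same rule in the PDI-only repeats. Limit the earliest-admission rule to discharge disposition and state that it means the index admission. Because this narrows the rule, the same edit should name the admission that supplies the other categorical rows of Table 24, such as ongoing hospitalization.

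The cost is a sentence or two in the SAP and a changed derivation. No new data are needed: Protocol 6.4.3 already requires a hospitalization visit for each later admission, with details of any reoperation and a utilization assessment at discharge.

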2.4. Exploratory Objectives

- To assess the efficacy of SA4Ag in the prevention of postoperative ISA disease occurring within 90 days of elective open posterior spinal fusion procedures with multilevel instrumentation, in adults 18 to <86 years of age.
- To assess the efficacy of SA4Ag in the prevention of postoperative ISA disease occurring within 180 days of elective open posterior spinal fusion procedures with multilevel instrumentation, in adults 18 to <86 years of age.
- To assess the efficacy of SA4Ag in the prevention of postoperative *S aureus* BSI and/or deep incisional or organ/space SSI occurring within 90 days of elective open posterior spinal fusion procedures with multilevel instrumentation, in adults 18 to <86 years of age, based on baseline *S aureus* colonization status.
- To assess the efficacy of SA4Ag in the prevention of postoperative *S aureus* BSI and/or deep incisional or organ/space SSI occurring within 180 days of elective open posterior

spinal fusion procedures with multilevel instrumentation, in adults 18 to <86 years of age, based on baseline *S aureus* colonization status.

- To describe the immunogenicity of SA4Ag in adults aged 18 to <86 years undergoing elective open posterior spinal fusion procedures with multilevel instrumentation.
- To describe *S aureus* colonization in adults aged 18 to <86 years undergoing elective open posterior spinal fusion procedures with multilevel instrumentation, before and after SA4Ag administration.
- To compare healthcare utilization data between vaccine groups.

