9.4.2. Healthcare Utilization

Healthcare utilization will be determined for each vaccine group and will include days in hospital, days in an ICU, discharge disposition, inpatient days in skilled nursing or rehabilitation facilities after discharge, number of readmissions to hospital, number of reoperations, days of antibiotic use, and outpatient visits for rehabilitation/physical therapy. Descriptive statistics will be calculated for each vaccine group. Two-sided 95% CIs for the mean or median difference between vaccine groups will be obtained where applicable (ie, not for categorical responses such as postdischarge disposition). Comparisons of healthcare use will be performed between vaccine groups for the per-protocol, mITT, and safety populations.

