### 8.2.3.3. Healthcare Utilization

All analyses will be performed in the mITT efficacy population. No subgroup analyses are proposed.

Healthcare variables will be reanalyzed, but limited to subjects adjudicated to have 1 of 3 endpoints (BSI and/or organ/space or deep incisional SSI, SSI, or ISA disease) crossed with 2 windows (1-90 and 1-180 days after surgery).

Healthcare utilization analyses are summarized in Table 24.

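### Facility days, service visits, therapy visits and ICU days are tested only among users, because SAP 8.1.3.3 assigns no zeros to non-users

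*SAP*

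**What the plan says.** The exploratory objective in Protocol 2.4 is: "To compare healthcare utilization data between vaccine groups". Protocol 9.4.2 adds: "Two-sided 95% CIs for the mean or median difference between vaccine groups will be obtained where applicable". It puts no users-only limit on the comparison.

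SAP 8.1.3.3 turns this into tests. It says "Healthcare utilization variables whose units are days (eg, number of days in an ICU) will be summarized by sample size", followed by the usual location and spread statistics, and then "Vaccine groups will be compared using the van Elteren test, with site as the stratification variable". Service visits and outpatient rehabilitation or physical therapy visits are also compared by van Elteren. SAP 8.2.3.3 names the population: "All analyses will be performed in the mITT efficacy population. No subgroup analyses are proposed". Table 24 gives the purpose as the effect of vaccination on later healthcare use.

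SAP 8.1.3.3 also contains the rule at issue: "Zeroes will not be imputed to subjects without the indicated response, eg, number of days in a skilled nursing facility".

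ICU days are restricted in two other places. SAP 6.3.3 lists "Number of days in the ICU, limited to subjects with hospital readmission related to complications for surgery". SAP 8.1.3.2 limits index-stay ICU days to subjects who were in intensive care, and readmission ICU days to subjects with any readmission. The two readmission denominators differ.

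**The concern.** A subject who was followed and never entered a nursing facility spent 0 days there. That is an observed value. If it is not entered, the subject has no value and leaves the rank test. What remains is a comparison of vaccine users with placebo users, and whether a subject becomes a user is itself an outcome after randomization. The mITT label then no longer describes the analysed set.

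What is at stake is the meaning of the comparison. One way a vaccine could lower healthcare use is to lower the number of people who need the service. A users-only test gives no credit for that, and it equally hides an excess of users in the vaccine group. It also mixes two effects: a change in how long users stay, and a change in who becomes a user.

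**Working it through.** **Is non-use observed?** Protocol Table 1 schedules healthcare-utilization collection at discharge and at Days 21, 42, 90 and 180. For a subject with those contacts, no recorded use is a known zero.

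**Which variables are affected?**

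| Variable | Has a value for nearly all mITT subjects without zeros? | Any-use test elsewhere |
|---|---|---|
| Hospital duration, total hospitalization | Yes; the index stay supplies a value unless coded ongoing | Not needed |
| ICU days | No | Index ICU use (SAP 8.1.3.2); ICU during readmission, among the readmitted |
| Rehabilitation or nursing-facility inpatient days | No | None; discharge disposition covers part |
| Service visits | No | None |
| Outpatient therapy visits | No | None |

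Readmission and complication-related readmission are tested by CMH (SAP 8.1.3.2, Table 24). Discharge disposition is also tested by CMH, but SAP 8.1.3.3 keeps only the earliest admission for categorical variables, so facility use after a later readmission is not captured. SAP 6.3.3 does not count discharge straight to a facility as a service visit.

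**Contrast within the SAP.** In SAP 8.1.2.4, transfusion counts include zero explicitly. Transfusion units are limited to recipients, but the proportion transfused is tested beside them.

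**Mechanism.** All-subject mean = (proportion using) × (mean among users). A users-only test sees only the second factor.

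**Illustration.** The documents give no utilization rate, length or SD, so there is no plan figure to reproduce and every rate and length below is an assumption. Arm size comes from Protocol 9.2: 6000 × 0.90 / 2 = 2700. That design reproduces: 48 / (0.45 × 0.014 × 1.3) = 5861 subjects at VE 70% (stated about 6000), and 48 / (0.45 × 0.014 × 1.4) = 5442 at VE 60% (stated about 5440).

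Days among users are lognormal with sigma 0.8, rounded up. The mean for median m is about m × exp(0.32) + 0.5 = 1.377m + 0.5. There were 1000 simulated trials per scenario, with a two-sided Mann-Whitney test at 0.05 as an unstratified stand-in for van Elteren. Use falls from 10% to 7% in each scenario.

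- A: all users have median 14 days.
- B: long stays (median 28) are 5% in both groups; short stays (median 7) fall from 5% to 2%.
- C: short stays are 5% in both groups; long stays fall from 5% to 2%.

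| Scenario | Mean among users, vaccine vs placebo | Users-only test: benefit / harm | All-subject mean, vaccine vs placebo | With zeros: benefit / harm |
|---|---|---|---|---|
| A | 19.8 vs 19.8 | 2.0% / 2.5% | 1.38 vs 1.98 | 97.6% / 0.1% |
| B | 30.7 vs 24.6 | 0.5% / 83.5% | 2.16 vs 2.47 | 80.8% / 15.5% |
| C | 18.3 vs 24.7 | 87.0% / 0.1% | 1.28 vs 2.47 | 98.2% / 0.0% |

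Hand check of B. Vaccine: (5 × 28 + 2 × 7) / 7 = 22, and 1.377 × 22 + 0.5 = 30.8. Placebo: (5 × 28 + 5 × 7) / 10 = 17.5, and 1.377 × 17.5 + 0.5 = 24.6.

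Significant results were classed as benefit or harm by the sample means. In B with zeros the rank test was significant in 80.8% + 15.5% = 96.3% of trials; in the 15.5%, the noisy sample mean was higher in the vaccine group.

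**Scale under the design.** With 1.4% placebo incidence and VE 70%, primary-endpoint infections fall by 1.4% × 0.70 = 0.98 points. If every prevented case would otherwise have been a user, use falls from an assumed 10% to 9.02%. The standard error is √[(0.10 × 0.90 + 0.0902 × 0.9098) / 2700] = 0.00798, z = 0.0098 / 0.00798 = 1.23, and power is about P(Z > 1.96 − 1.23) = 23%. A simulation with half of infected subjects using the service and background use of 2% or 10% gave benefit in 6% to 18% of trials with zeros. Users-only gave benefit in 1% to 11% and harm in 0.2% to 6%.

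**The case against.** The rule can be read more mildly: an absent record is not to be assumed zero, while a recorded 0 stays. Where the SAP restricts ICU days it says so, and no such restriction is written for facility days, service visits or therapy visits. This reading is possible. However, the rule's own example is skilled-nursing days, where most subjects would be expected to have no stay, and the rule does not separate non-use from missing follow-up. If only missing data were meant, the sentence still needs rewriting.

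A stronger objection is that any-use tests together with days among users form a reasonable two-part analysis. That stands for readmission, index ICU use and discharge disposition. It does not stand for post-discharge facility stays, service visits or therapy visits, which lack the first part. The re-analysis limited to subjects with a protocol-defined infection does not supply it, since it also selects on a post-randomization event.

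A reader might infer that the rule makes an effective vaccine look useless or harmful. The documents do not support that as a general statement. Reversal needs mainly short uses to be prevented. Protocol 1.2.1 reports about three times the hospital stay for inpatients with *S aureus* infection, which points towards long uses, as in scenario C, where users-only testing still favoured the vaccine. Nor do the documents support the large power losses in A as a forecast: a 3-point fall in use is well beyond the 0.98 points that the design implies for primary-endpoint infections.

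**Conclusion.** Wrong as written, limited to an exploratory objective. For rehabilitation or nursing-facility days, service visits, outpatient therapy visits and ICU days, the planned test compares groups formed after randomization and does not answer the stated objective. The direction of the distortion is not fixed: it can remove, keep or reverse a difference, depending on which uses are prevented.

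The size cannot be known from the documents. The simulated figures rest on assumed use rates, assumed lengths, an unstratified test and the planned 2700 per arm, whereas SAP 8.1.3.5 records that enrollment ceased for futility. At the design infection rates power is low with either rule, so adding zeros restores the right comparison more than it gains sensitivity. It would be wrong to infer that all healthcare-use results are affected, or that any primary, secondary or safety conclusion is. Hospital duration and total hospitalization are unaffected.

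**What to change.** Replace the sentence in SAP 8.1.3.3 with a rule along these lines:

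- For mITT subjects with observed follow-up and no recorded use, set days or visits to 0. Leave unobserved follow-up missing.
- State how deaths and early dropouts are handled, since an early death would otherwise score as low use. For example, report them alongside and add a sensitivity analysis per day of follow-up.
- Run the van Elteren test over all mITT subjects.
- Report the proportion with any use and the days among users as description, without a test.
- Align the ICU-day definitions in SAP 6.3.3 and 8.1.3.2 with this rule and with each other; changing 8.1.3.3 alone would leave those restrictions in place.

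The cost is a short paragraph, one derivation rule per variable and two wording changes. No new data collection is needed. If group-level data have already been seen, date the change and show the users-only result beside the new one.
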